6.2 RESPONSE DEFINITIONS

6.2.1 Response

Response criteria are defined in Appendix 2. Response will be recorded at day +28 and day +56. Best response will also be recorded: i.e. the maximum improvement achieved following BMSC infusion in the follow up period between day +56 and one year post transplantation.

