The Cell Processing Section of the Department of Transfusion Medicine at the Clinical Center NIH has developed a BMSC repository at NIH. The NIH BMSC are a third party, early passage product based on the EU manufacturing approach. The NIH BMSC cellular product was administered safely to transplant recipients with steroid-resistant acute GVHD in a phase I study (protocol 12-H-0010, IND #14596) conducted from March 2012 to October 2012 at NIH. This pilot study is a continuation of the previous study and open to allogeneic stem cell transplantation recipients at NIH (age ≥ 4 yrs) with *de novo* acute GVHD requiring systemic therapy, either directly after allogeneic transplantation or following treatment with donor lymphocyte infusion. Subjects will receive BMSC infusions (target dose of 2×10^6 BMSC/kg for up to 12 doses) in addition to standard upfront therapy with corticosteroids. The primary endpoint will be the proportion of patients without a treatment-related severe adverse event (TRSAE) at day +56. Responses will be assessed at day +28 and +56 from the initial diagnosis. Responses will be correlated to changes in GVHD biomarkers including ST2, Reg3a, TNFR1, and IL-6. Subjects will be enrolled at first diagnosis of acute GVHD, and the first BMSC infusion will be given within 120 hours of the first dose of corticosteroids. BMSC infusions will be given twice weekly for the first 4 weeks. Subjects with a complete response at the end of week 4 will not receive further infusions. All other subjects will receive BMSC infusions weekly for four additional weeks. Safety will be monitored continuously with a stopping rule for toxicity based on the treatment-related serious adverse event rate. Research samples will be drawn at regular intervals to explore biological correlates of response and to investigate the mechanism of action of BMSC.

Abbreviated Title: Early BMSC Pilot for Acute GVHD

Version Date: 6/16/2016

TABLE OF CONTENTS

1. INTRODUCTION	5
1.1 Study Objectives	5
2. BACKGROUND	5
2.1 Acute Graft-versus-Host Disease	5
2.2 Primary Therapy for Acute GVHD	6
2.3 Biology of Bone marrow-derived mesenchymal stem cells.....	6
2.4 Clinical Experience With BMSC in GVHD	7
2.5 NIH Phase I BMSC Trial (12-H-0010).....	10
2.6 Safety Of BMSC Infusions	11
2.7 Scientific And Clinical Justification	12
2.8 Rationale for Changes from Phase I Study	12
3. STUDY DESIGN.....	14
3.1 Study Design	14
3.2 Subject Inclusion	14
3.3 Initial Assessment	14
3.4 Treatment	15

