3.2 SUBJECT INCLUSION

Provided subjects satisfy inclusion criteria in Section 5.1, the protocol is open to all subjects transplanted at NIH who are diagnosed with acute GVHD, irrespective of conditioning regimen, primary disease, or transplant type. The protocol will include subjects at any time after allogeneic stem cell transplantation.

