3.6 RESPONSE

Subjects will be assessed for response for the primary indication according to criteria listed in Appendix 2. The critical time points for response are at day +28 and day +56. Subjects are considered off protocol after 11 weeks of total enrollment. Subjects will receive additional infusions after day +28 based upon whether or not there is a complete response at the day +28 response assessment (Section 3.4.1). After coming off protocol, subjects will be followed for best response for up to 1 year on their parent transplant protocols.

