7. SAMPLE COLLECTION, STORAGE AND TRACKING PLAN

7.1 RESEARCH SAMPLE COLLECTION

All research sampling will be obtained based upon the clinical situation and may be optional at the discretion of the PI. Such situations may occur without violating the protocol when the PI determines that sample collection is precluded by the subject's performance status, or would interfere with management of an acute medical situation or when logistic considerations prevent procurement or processing of the specimen.

7.1.1 Research Blood Sampling:

Research blood samples: 54 mL of blood will be drawn [1 (6 ml) lavender top- K2-EDTA for plasma and 6 (8 ml) red-green "tiger top"] on Day 0 (pre BMSC infusion), Day 28, and Day 56. 3 mL of blood [1 (3 ml) lavender top- K2-EDTA for plasma] will be drawn before and after each BMSC infusion (+/- 24 hours) and at 3 weeks after the last infusion (+/- 7 days). Testing will include for cytokines, GVHD biomarkers, plasma exosomes, lymphocyte subset analysis and other Stem Cell Allotransplantation Section research studies (Appendix 3). For logistic considerations, a +/- 3-day window can be applied to sample draw dates on D0, D28, and D56. Blood will be stored at room temperature and transported to the laboratory of [name], NHLBI, NIH for analysis. A list of IRB-approved research tests that will be conducted on the collected samples is included in Appendix 4.

Pharmacokinetics (PKs): In selected patients, and after selected infusions (as determined by the investigator, clinical course, and available nursing/lab resources), up to 10 blood samples will be drawn for PKs to determine the kinetics of BMSC-derived exosome release. 2mL of blood in 3mL lavender top- K2-EDTA tubes will be drawn at intervals following infusion. The suggested intervals are 20 min, 40 min, 1 hr, 2 hrs, 4 hrs, 6 hrs, 8 hrs, 12 hrs, 18 hrs, and 24 hrs from infusion. The suggested intervals are not mandatory and can be modified as needed based on nursing/laboratory availability and clinical course.

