9.1.2 Completion of Infusions

A maximum of 12 infusions is planned. Final evaluation of outcomes and response to the BMSC will occur 3 weeks after the last infusion. After planned infusions and the three week monitoring period, subjects will be taken off protocol. Subjects will be followed for GVHD response and survival as a secondary endpoint for up to 1 year on their parent transplant protocol.

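### The best-response window in section 6.2.1 opens on the study clock and closes on the transplant clock, so it drops responses lost before day +56 and can be short or empty for late entrants

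*Combined protocol and SAP*

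**What the plan says.** Section 6.2.1 first fixes two visits: "Response will be recorded at day +28 and day +56". It then adds best response, defined as "the maximum improvement achieved following BMSC infusion in the follow up period between day +56 and one year post transplantation".

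Two other sections describe the later follow-up:

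- Section 3.6: "After coming off protocol, subjects will be followed for best response for up to 1 year on their parent transplant protocols".
- Section 9.1.2: "Subjects will be followed for GVHD response and survival as a secondary endpoint for up to 1 year", again on the parent transplant protocol.

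Neither of these ties the year to the transplant date.

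On entry, section 3.2 states: "The protocol will include subjects at any time after allogeneic stem cell transplantation". Section 5.1.1 admits acute GVHD arising more than 100 days after transplant or DLI, and sets no limit on the interval from transplant to DLI.

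Section 11.2 lists the CR, PR, MR, NR and worsening proportions at day +28 and day +56 as secondary endpoints. Best response is not in that list, and section 11.3.1 gives no analysis specific to it.

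**The concern.** The two ends of the window are measured from different origins. The opening moves with the subject's entry to the study. The closing is fixed by the transplant date. The longer the gap between transplant and entry, the less time a subject has in which a best response can be observed, and for a late enough entry the window closes before it opens.

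The opening end has a separate problem. A variable called best response would normally be at least as good as any response recorded during treatment. Here the first 56 days after entry do not count. They contain the day +28 assessment and are also the most closely observed period: Appendix 3 requires GVHD evaluation at least weekly for 56 days, whereas section 6.1.4 leaves follow-up after the last infusion to the subject's condition.

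At stake is whether a reported best-response proportion means the same thing for each subject, and whether two analysts working from sections 3.6, 6.2.1 and 9.1.2 would derive the same value. With 23 evaluable subjects, each one classified differently moves a proportion by 1/23, or about 4 percentage points.

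**Working it through.** The plan states no figure for the length of this window, so there is nothing to reproduce. The check is calendar arithmetic.

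**Inputs**

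- Window opens at study day +56 and closes one year after transplant, taken as 365 days (6.2.1).
- T = days from transplant to Day 0. There is no upper limit (3.2, 5.1.1) and no distribution is given, so the values of T below are assumed.
- Origin of the study clock. The synopsis says "Responses will be assessed at day +28 and +56 from the initial diagnosis"; section 7.1.1 lists "Day 0 (pre BMSC infusion), Day 28, and Day 56". The synopsis also says "the first BMSC infusion will be given within 120 hours of the first dose of corticosteroids", so the two origins can differ by up to 5 days if diagnosis and first steroid dose fall together.

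**Closing end**

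If T is counted to the event that starts the study clock:

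W = 365 − (T + 56) = 309 − T.

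If T is counted to diagnosis or first steroid dose, but the clock starts at a first infusion 5 days later:

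W = 365 − (T + 5 + 56) = 304 − T.

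| T (days) | 309 − T | 304 − T |
|---|---|---|
| 30 | 279 | 274 |
| 100 | 209 | 204 |
| 101 | 208 | 203 |
| 200 | 109 | 104 |
| 250 | 59 | 54 |
| 300 | 9 | 4 |
| 304 | 5 | 0 |
| 309 | 0 | −5 |
| 365 | −56 | −61 |

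A negative value means that the window closes before it opens. A post-DLI illustration with assumed times: DLI 280 days after transplant and GVHD treated on study 40 days later gives T = 320 and W = 309 − 320 = −11. In section 5.1.1 such a subject has classic acute GVHD, being within 100 days of DLI. Under 6.2.1 the subject has no best response.

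**Opening end**

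- CR at day +28, flare by day +56, CR regained within the window: best response is CR, as expected.
- CR at day +28, flare by day +56, CR not regained: best response is worse than the day +28 record. Section 3.4.4.3 foresees flares during taper, so the case is realistic.
- Response followed by death before day +56: no best response.
- Response that persists past day +56 in a subject with an open window: counted normally.

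**Comparison with 3.6 and 9.1.2**

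Suppose the year in 3.6 starts when the subject comes off protocol. Using the 7 to 11 weeks of monitoring in section 11.2, follow-up ends 49 + 365 = 414 to 77 + 365 = 442 days after first infusion, whatever T is. Under 6.2.1 it ends 365 − T days after Day 0, for example day 265 at T = 100. On that reading the statements do not agree.

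**The case against.** The strongest reply is that best response is a supplementary item. Section 3.6 treats day +28 and day +56 as the key response times, section 11.2 lists only those, and 6.2.1 says best response is recorded in addition. On that view it is a late-follow-up measure with a misleading label, and an overall best can be rebuilt from the recorded values. This stands to a large extent: a day +28 CR is not lost from the data, and the listed day +28 endpoint still counts it. It does not rescue the definition, which as worded can return a best response below one already recorded, or none at all.

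Four stronger readings are tempting and the documents do not support them.

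- *Every late-onset or post-DLI subject has a short or empty window.* Onset at day 101 leaves 208 days, and an early DLI can leave a similar period. Section 2.1 says acute GVHD mostly arises within 100 days of transplant, which leaves 209 days or more under the first formula.
- *Section 9.1.2 makes best response a secondary endpoint.* It refers to GVHD response and survival generally, and 11.2 does not list best response.
- *Section 3.6 states a conflicting end date outright.* It does not say where its year starts; counting from coming off protocol is the natural reading, but not an explicit one.
- *Unequal windows bias a comparison.* This is a single-arm pilot with no planned between-subject comparison of best response.

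**Conclusion.** The point holds as a defect in a stated rule. The window runs 309 − T days, falls below 60 days from T = 250, and is empty from about T = 304 to 309 depending on the clock origin. It also excludes any response gained and lost before day +56, whatever T is. Nothing elsewhere in the document repairs this, and sections 3.6 and 9.1.2 do not carry the transplant anchor.

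The size is modest. How many of the 23 to 25 subjects would be affected cannot be computed, because time from transplant to entry is not described; it could be none. The outcome is descriptive and outside the 11.2 list. The primary endpoint (reaching day +56 without a TRSAE), the sample size and the stopping rule do not depend on it.

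The figures assume a 365-day year, a window read literally from 6.2.1, and an offset between clock origins of at most 5 days.

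**What to change.** In 6.2.1, define best response as the maximum improvement from baseline at any assessment from the first BMSC infusion, including the day +28 and day +56 assessments, up to one fixed time on the study clock that is the same for every subject. One year after Day 0 is a suitable example. Use the same start and end in 3.6 and 9.1.2, and name the event that defines Day 0.

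The cost is about one sentence in each of the three sections. The early responses are already recorded. If the year in 3.6 runs from coming off protocol, day 365 falls inside follow-up already planned (day 414 to 442 after first infusion). Section 7.2.4 also lets the study stay open for up to a year after the last subject completes treatment.

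The downside is that one year after Day 0 falls T days beyond the transplant anniversary. That is a small extension for early entrants and a long one for late entrants. The parent protocols are not in the document, so whether they collect response that far out is unknown. Where they do not, report the subject's follow-up as truncated, with its length.

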7. SAMPLE COLLECTION, STORAGE AND TRACKING PLAN

7.1 RESEARCH SAMPLE COLLECTION

All research sampling will be obtained based upon the clinical situation and may be optional at the discretion of the PI. Such situations may occur without violating the protocol when the PI determines that sample collection is precluded by the subject's performance status, or would interfere with management of an acute medical situation or when logistic considerations prevent procurement or processing of the specimen.

7.1.1 Research Blood Sampling:

Research blood samples: 54 mL of blood will be drawn [1 (6 ml) lavender top- K2-EDTA for plasma and 6 (8 ml) red-green "tiger top"] on Day 0 (pre BMSC infusion), Day 28, and Day 56. 3 mL of blood [1 (3 ml) lavender top- K2-EDTA for plasma] will be drawn before and after each BMSC infusion (+/- 24 hours) and at 3 weeks after the last infusion (+/- 7 days). Testing will include for cytokines, GVHD biomarkers, plasma exosomes, lymphocyte subset analysis and other Stem Cell Allotransplantation Section research studies (Appendix 3). For logistic considerations, a +/- 3-day window can be applied to sample draw dates on D0, D28, and D56. Blood will be stored at room temperature and transported to the laboratory of [name], NHLBI, NIH for analysis. A list of IRB-approved research tests that will be conducted on the collected samples is included in Appendix 4.

Pharmacokinetics (PKs): In selected patients, and after selected infusions (as determined by the investigator, clinical course, and available nursing/lab resources), up to 10 blood samples will be drawn for PKs to determine the kinetics of BMSC-derived exosome release. 2mL of blood in 3mL lavender top- K2-EDTA tubes will be drawn at intervals following infusion. The suggested intervals are 20 min, 40 min, 1 hr, 2 hrs, 4 hrs, 6 hrs, 8 hrs, 12 hrs, 18 hrs, and 24 hrs from infusion. The suggested intervals are not mandatory and can be modified as needed based on nursing/laboratory availability and clinical course.

7.2 COLLECTION, STORAGE AND DISPOSITION OF SAMPLES

7.2.1 Intended use

Any research specimen will not be read by a pathologist or used for diagnostic purposes. These studies will not be used in assessing clinical endpoints but are undertaken for descriptive or exploratory ancillary research.

Abbreviated Title: Early BMSC Pilot for Acute GVHD

Version Date: 6/16/2016

7.2.2 Tracking

Samples will be ordered and tracked through the CRIS Research Screens. Should a CRIS screen not be available, the NIH form 2803-1 will be completed and will accompany the specimen and be filed in the medical record. Samples will not be sent outside NIH without IRB notification and an executed MTA.

7.2.3 Storage

Research samples will be stored with identifiers in the secure laboratory of [name], NHLBI, NIH. Specimens will be entered in the NHLBI Biospecimen Inventory System (BSI).

7.2.4 End of study procedures

The study will remain open so long as sample or data analysis continues to a maximum of one year after the last subject completes treatment. Samples from consenting subjects will be stored until they are no longer of scientific value or if a subject withdraws consent for their continued use, at which time they will be destroyed.

7.2.5 Loss or destruction of samples

Should we become aware that a major breach in our plan for tracking and storage of samples has occurred, the IRB will be notified.

8. MANAGEMENT OF COMPLICATIONS

8.1 OVERVIEW

Serious toxicities related to infusion of BMSC have not been reported. Hives and nasal congestion have been identified infrequently. Infusion associated fever is recognized. As with any infusion of a cell product, immediate transfusion reactions are a theoretical possibility.

8.2 IMMEDIATE TRANSFUSION REACTION

Administration of BMSC will be performed according to NIH Clinical Center standard operating procedure: [Administration of Products of Cellular Therapy](#). If an allergic or other acute reaction occurs, studies appropriate for investigation of a transfusion reaction will be performed (urinalysis, CBC, Coomb's test). Any adverse reactions should prompt interruption of the infusion and should be reported to the principal investigator.

No further BMSC infusions will be administered to a subject in the event of:

- recurrent infusion related toxicity *despite premedication* (moderate toxicity is defined as requiring interruption or discontinuation of BMSC administration, which is not rapidly responsive to symptomatic medication)
- any CTCAE v4.0 grade 4 acute infusion reaction (defined as requiring discontinuation of infusion AND urgent cardiopulmonary intervention) or grade 4 hypersensitivity reaction (anaphylaxis) at least possibly related to BMSC infusions
- any CTCAE v4.0 grade 3 infusion reaction that does not resolve completely within 2 hours
- any CTCAE v4.0 grade 3 acute infusion reaction or hypersensitivity that recurs when the infusion is restarted.

*Abbreviated Title: Early BMSC Pilot for Acute GVHD**Version Date: 6/16/2016*

8.3 TREATMENT LIMITING TOXICITIES

The observational period for determining Treatment Limiting Toxicities is from the initiation of the BMSC infusion to 3 weeks after the last infusion. A treatment related serious adverse event (TRSAE) is defined as an SAE which is at least probably or definitely related to the BMSC infusions. Any subject who encounters a TRSAE will not receive further infusions.

8.4 POST-TRANSPLANT COMPLICATIONS

New post-transplant complications will be managed according to standard NIH Intramural transplant guidelines (See [PBSCT Supportive Care Guidelines](#)).

9. OFF TREATMENT AND OFF STUDY CRITERIA

9.1 OFF TREATMENT CRITERIA

Subjects will receive no further BMSC infusions if any of the following occur:

9.1.1 Toxicity

Subjects experiencing BMSC infusion reaction as defined in Section 8.2 will receive no further BMSC infusions; subjects experiencing a grade 4 acute infusion reaction or hypersensitivity reaction will receive no further treatments; subjects experiencing a grade 3 acute infusion reaction or hypersensitivity reaction will receive no further treatments if symptoms do not resolve within 2 hours; subjects experiencing a grade 3 acute infusion reaction or hypersensitivity reaction will receive no further treatments if symptoms recur when infusion is restarted. Any subject who encounters a TRSAE will not receive further infusions. Subjects will be followed until off study criteria are met.

9.1.2 Completion of Infusions

A maximum of 12 infusions is planned. Final evaluation of outcomes and response to the BMSC will occur 3 weeks after the last infusion. After planned infusions and the three week monitoring period, subjects will be taken off protocol. Subjects will be followed for GVHD response and survival as a secondary endpoint for up to 1 year on their parent transplant protocol.

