11. BIOSTATISTICAL CONSIDERATIONS

11.1 PRIMARY ENDPOINT

The primary endpoint of this study is:

- The proportion of subjects reaching day +56 without a TRSAE.

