11.2 Secondary Endpoints

Secondary endpoints for this study are:

- Proportions of complete response (CR), partial response (PR), mixed response (MR), no response (NR), and worsening disease (WD) among surviving patients at day +28 and +56 of study (Appendix 2). Need for secondary immunosuppression by day +28 and +56 of study. Steroid dose (prednisone equivalent) at day +28 and +56 of study. Proportion of responses in patients with high and low ST2 levels.

Secondary endpoints will not be used in assessing success or failure of the primary endpoint but are undertaken for descriptive or exploratory research and will be reported accordingly. The duration of treatment limiting toxicity monitoring will be 3 weeks after the last dose of BMSC. The total duration of treatment limiting toxicity monitoring will be 7-11 weeks. Total serious adverse event monitoring will continue until at least 3 weeks after the last dose of BMSC, and subjects experiencing adverse events related to BMSC will be monitored until toxicity resolution or stabilization.

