11.3.2 Sample Size

Let p be the probability of subjects reaching day +56 without a TRSAE. The sample size is determined by testing the null hypothesis $H_0 : p = 75\%$ versus the alternative hypothesis $H_a : p > 75\%$ with a one-sided significant level of 0.05. Based upon our previous phase 1 trial (12-H-0010), the TRSAE rate was 0 out of 10 subjects and we expect 95% subjects would reach day +56 without a TRSAE. Thus a sample size of 23 subjects will achieve 89.5% power to test the above hypotheses using an exact binomial test.

To account for the possibility of non-treatment related drop out, up to 2 additional subjects may be enrolled to replace those subjects that are non-evaluable for the study's primary endpoint for a total accrual of 25 patients. At an accrual rate of 1-2 subjects per month, this study will be completed in 12-18 months.

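### Section 9.1.2 lets a complete responder go off protocol before the day +56 primary endpoint, and other sections say otherwise

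*Combined protocol and SAP*

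**What the plan says.** **The endpoint.** Section 11.1 defines it as "The proportion of subjects reaching day +56 without a TRSAE", and 11.3.2 tests the same quantity: "Let p be the probability of subjects reaching day +56 without a TRSAE". Neither states day 0. The opening summary counts response days from initial diagnosis. Section 7.1.1 and Appendix 3 place Day 0 just before the first infusion.

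**Text that allows follow-up to stop early.**
- The opening summary: "Subjects with a complete response at the end of week 4 will not receive further infusions".
- 8.3 sets the observation period for treatment-limiting toxicities "from the initiation of the BMSC infusion to 3 weeks after the last infusion". It defines the TRSAE in the same paragraph and gives no other TRSAE window.
- 9.1.2 puts the final evaluation 3 weeks after the last infusion, then: "After planned infusions and the three week monitoring period, subjects will be taken off protocol". For the time after that: "Subjects will be followed for GVHD response and survival as a secondary endpoint", on the parent transplant protocol. TRSAEs are not named.
- 11.2: "The total duration of treatment limiting toxicity monitoring will be 7-11 weeks".
- 6.1.4 leaves evaluations after the last infusion to the subject's condition.

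**Text that points to longer follow-up.**
- 3.5 uses an 11-week toxicity window, and 3.6 takes subjects off protocol at 11 weeks.
- The Appendix 3 adverse-event row is marked through weeks 5-7 and Day 56.
- Day +56 assessments appear in 3.7 (survival), 6.2.1 (response), 7.1.1 (research blood) and 11.2 (response, steroid dose, secondary immunosuppression).
- 11.2 on SAEs generally: "Total serious adverse event monitoring will continue until at least 3 weeks after the last dose of BMSC".

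None of these makes an exception for complete responders.

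**The concern.** Day +56 is 8 weeks, while the lower end of the monitoring period in 11.2 is 7 weeks. The 7-week subjects are the complete responders: 4 weeks of infusions plus 3 weeks. Sections 3.6 and 9.1.2 give the same subject two different off-protocol times, and staff cannot follow both.

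If 9.1.2 is the one followed, a complete responder's status at day +56 may not be observed. This is the only primary endpoint, and the test has little slack (attained alpha 0.049 against a nominal 0.05). The plan is also silent on how such a subject would enter the analysis. Counting the subject as TRSAE-free could only help the trial to declare safety. Treating the subject as non-evaluable would reduce the number analysed, and 11.3.2 provides for only 2 replacements (25 accrued for 23 evaluable).

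**Working it through.** **1. The plan's own figures.** With n = 23, a null of 75% and an alternative of 95% TRSAE-free (11.3.2), and rejection at 21 or more of 23 (11.3.4.2):
- alpha = P(Bin(23, 0.25) ≤ 2) = 0.0492
- power = P(Bin(23, 0.05) ≤ 2) = 0.8948, which is the stated 89.5%
- a cut-off of 20 would give alpha 0.137, so 21 is correct.

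The 7-11 weeks in 11.2 also reproduce: 4 + 3 = 7 weeks (day 49) and 8 + 3 = 11 weeks (day 77).

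**2. When the 3-week period ends for a complete responder.** Section 3.4.1 gives eight doses twice weekly, usually on Tuesday and Friday.

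| Last infusion, counted from the first | End (+21 days) | Short of day 56 by | End counted from diagnosis (+5 days) | Short by |
|---|---|---|---|---|
| Day 24 (Tuesday start) | 45 | 11 | 50 | 6 |
| Day 25 (Friday start) | 46 | 10 | 51 | 5 |
| Day 28 (end of week 4) | 49 | 7 | 54 | 2 |

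The 5-day shift assumes that steroids start at diagnosis and that the full 120 hours in 3.4.1 are used. The ±7-day window that Appendix 3 puts on the 3-week visit moves that visit either way: day 38-52 around day 45, or day 42-56 around day 49. Subjects without a complete response are monitored to about day 70-77 and are covered.

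**3. Effect on alpha if early leavers count as TRSAE-free.** The assumptions are:
- the true day-56 TRSAE risk is 0.25 (the null);
- 50% are complete responders;
- day 0 is the first infusion;
- the hazard is constant up to the last infusion on day L and k times that value afterwards.

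Risk observed in complete responders by day L + 21:

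r = 1 − 0.75^[(L + 21k) / (L + k(56 − L))]

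Overall observed risk is q = 0.5r + 0.5 × 0.25, and attained alpha is P(Bin(23, q) ≤ 2).

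| Hazard after last infusion | r (L = 24 / 28) | q | Attained alpha |
|---|---|---|---|
| none (k = 0) | 0.2500 / 0.2500 | 0.2500 / 0.2500 | 0.049 / 0.049 |
| 10% (k = 0.1) | 0.2412 / 0.2451 | 0.2456 / 0.2475 | 0.054 / 0.052 |
| constant (k = 1) | 0.2064 / 0.2225 | 0.2282 / 0.2363 | 0.077 / 0.066 |

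Counted from diagnosis with the 5-day delay, the same three rows give 0.049, 0.050-0.051 and 0.053-0.063.

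**4. If early leavers are non-evaluable.** Alpha is not raised by this route. The cost is that more than 2 such subjects leave fewer than the 23 evaluable that the power calculation needs.

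**The case against.** Much can be said for the plan.

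- **The early window is not expressly a TRSAE window.** Section 8.3 and the 7-11 weeks in 11.2 concern treatment-limiting toxicities. A TRSAE is an SAE, and the SAE rule in 11.2 is a floor that permits follow-up to day +56. This stands. But the floor does not require such follow-up, and 8.3 gives TRSAEs no other window.
- **Subjects have day +56 contacts.** A serious event in the preceding 7-11 days would probably come to light at the Day 56 assessments, and 12.4 sets no cut-off for reporting SAEs to the sponsor. This also stands, and it is why loss of data is not certain. It does not settle which of 3.6 and 9.1.2 applies.
- **Off protocol may not mean off study.** Section 9.1.2 sits under the off-treatment criteria, and 9.2 does not list the 3-week point. That is a fair reading. Yet 3.6 uses the same off-protocol term with a different time, and 9.1.2 limits what is followed afterwards.

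Three stronger conclusions are tempting but not supported:

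- **That TRSAEs will be missed.** Appendix 3, if followed, captures them.
- **That the test is biased toward declaring safety.** No passage says that a subject taken off early counts as TRSAE-free. The alpha figures above depend on that assumption.
- **That the stopping rule in 11.3.4.2 is wrong when it equates 3 subjects with a TRSAE with non-rejection.** It refers to the test in 11.3.2, which is a day +56 test, and on that reading the statement is correct. Limiting the tally to events by day +56 would also exclude later TRSAEs from the safety stop.

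**Conclusion.** The contradiction is real and concerns ascertainment of the primary endpoint. Under 9.1.2 a complete responder can go off protocol 7-11 days before day +56 (day 0 at the first infusion), or 2-6 days before it (day 0 at diagnosis, 5-day delay). Sections 3.5 and 3.6, Appendix 3 and the day +56 assessments imply otherwise.

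The likely effect is small. Under the stated assumptions, attained alpha runs from 0.049 to 0.077. The toxicities named in 8.1, 13.3.1 and 14.1.2 are infusion-type reactions, which points to the low end (0.049-0.054). Section 2.6 also names susceptibility to infection, which need not end with the infusions, so a zero effect is not assured. The share of complete responders, the hazard shapes and the TRSAE-free classification are assumptions that the documents do not supply. The point should be corrected because the remedy is nearly free, not because the design fails.

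**What to change.** - Keep the day +56 endpoint and state its day 0 in 11.1.
- Amend 9.1.2, and align 8.3 and 11.2, so that TRSAE follow-up of every subject runs to the later of day +56 and 3 weeks after the last infusion. No subject should be taken off protocol before then except under 9.2.
- Reconcile 3.5, 3.6, 6.1.4 and Appendix 3 with that rule.
- Leave 11.3.4.2 as it is.

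The change is wording only. N = 23, the 21-of-23 rule, alpha 0.049 and power 89.5% stay as they are. The cost is 1-2 more weeks of SAE follow-up for complete responders, which Appendix 3 already marks.
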